5.2.3.4 Rescue Therapy

For subjects re-randomized to placebo, ABT-494 7.5 mg QD or ABT-494 15 mg QD in Period 2, blinded rescue therapy with ABT-494 30 mg QD will be provided after the first instance of a < EASI 50 response starting at the Week 20 visit (4 weeks after re-randomization into Period 2). These subjects will continue on ABT-494 30 mg QD for the remainder of the study.

During Period 2, concomitant class III – IV, medium potency topical corticosteroid treatment will be permitted at the Week 24 visit and thereafter in subjects after a second instance of < EASI 50 response in any two Period 2 study visits beginning from Week 20. For subjects who receive topical corticosteroid rescue therapy, an additional visit will be

required 4 weeks after receiving topical corticosteroid rescue therapy. Discontinuation from study drug will be mandatory for subjects with < EASI 50 response compared with their Baseline EASI score 4 weeks following rescue with topical corticosteroids or at any visit thereafter.

Topical treatment allowed is limited to up to twice daily triamcinolone acetonide 0.1% cream or up to once daily mometasone furoate 0.1% cream. Use of a topical corticosteroid treatment should be recorded on the appropriate concomitant medication eCRF.

5.2.4 Contraception Recommendations

Contraception Recommendation for Females

A woman who is postmenopausal or permanently surgically sterile (bilateral oophorectomy, bilateral salpingectomy or hysterectomy) is not considered to be a woman of childbearing potential and is not required to follow contraception recommendations.

Postmenopausal is defined as:

- Age \geq 55 years with no menses for 12 or more months without an alternative medical cause; or
- Age < 55 years with no menses for 12 or more months without an alternative medical cause AND a follicle-stimulating hormone (FSH) level > 40 IU/L.

If the female subject is < 55 years of age:

AND has had no menses for \geq 12 months AND has no history of permanent surgical sterilization (defined above), FSH should be tested at Screening.

- If FSH is not tested, it is assumed that the subject is of childbearing potential and protocol-specified contraception is required.
- If the FSH is tested and the result is consistent with post-menopausal status, contraception is not required.

- If the FSH is tested and the result is consistent with pre-menopausal status, contraception is required, and a serum pregnancy test must be performed (see Section 5.3.1.1 pregnancy test).

For a female subject at any age:

- Female subjects with menses within the past 12 months are of childbearing potential and FSH is therefore not required but contraception is required.
- Female subject who are surgically sterile (defined above) are not of childbearing potential and therefore no FSH testing or contraception is required.

A woman who does not meet the definition of postmenopausal or permanently surgically sterile is considered of childbearing potential and is required to practice at least one of the following highly effective methods of birth control that is effective from Study Day 1 (or earlier) through at least 30 days after the last dose of study drug.

- Combined (estrogen and progestogen containing) hormonal contraception (oral, intravaginal, transdermal) associated with the inhibition of ovulation, initiated at least 30 days prior to Baseline Visit.
- Progestogen-only hormonal contraception (oral, injectable, implantable) associated with inhibition of ovulation, initiated at least 30 days prior to Baseline Visit.
- Bilateral tubal occlusion/ligation (Japan only: bilateral tubal ligation only).
- Vasectomized partner(s) provided the vasectomized partner has received medical confirmation of the surgical success and is the sole sexual partner of the women of childbearing potential trial participant.
- Intrauterine device (IUD).
- Intrauterine hormone-releasing system (IUS).
- True abstinence: Refraining from heterosexual intercourse when this is in line with the preferred and usual lifestyle of the subject (periodic abstinence e.g., calendar, ovulation, symptothermal, post-ovulation methods] and withdrawal are not acceptable).

If required per local practices, male or female condom with or without spermicide OR cap, diaphragm or sponge with spermicide should be used in addition to one of the birth control methods listed above (excluding true abstinence).

Additional local requirements may apply. Refer to [Appendix P](#) for local requirements in Canada.

Contraception Recommendation for Males

For a male subject who has a female partner who is postmenopausal or permanently sterile, no contraception is required.

A male subject who is sexually active with female partner(s) of childbearing potential must agree from Study Day 1 through 30 days after the last dose of study drug to practice contraception with:

- Condom use and female partner(s) using at least one of the contraceptive measures (as defined in the protocol for female study subjects of childbearing potential).
- OR
- True abstinence: Refraining from heterosexual intercourse-when this is in line with the preferred and usual lifestyle of the subject. (Note: Periodic abstinence [e.g., calendar, ovulation, symptothermal, post-ovulation methods] and withdrawal are not acceptable).

Additionally, male subjects must agree not to donate sperm from the Baseline Visit through 30 days after the last dose of study drug.

Male subjects are responsible for informing his partner(s) of the risk of becoming pregnant and for reporting any pregnancy to the study doctor. If a pregnancy occurs, a partner authorization form requesting pregnancy outcome information will be requested from the pregnant partner.

It is important to note that contraception recommendations described above are specifically intended to prevent pregnancy during exposure to the investigational therapies.

Additional local requirements may apply. Refer to [Appendix P](#) for local requirements in Canada.

5.3 Efficacy, Pharmacokinetic, Specific Cellular Pharmacodynamic Changes, Exploratory Research and Validation Studies, and Safety Assessments/Variables

5.3.1 Efficacy and Safety Measurements Assessed and Flow Chart

Study procedures described are listed in the following section of this protocol and are summarized in tabular format in [Table 2](#).

Table 2. Study Activities

Activity	Screening D -35 to D -1	BL	Wk 2	Wk 4	Wk 8	Wk 12	Wk 16	Wk 20	Wk 24	Wk 32	Wk 40	Every 12 Weeks ^x or PD ^a	4 Weeks Post Topical Rescue Visit ^y	30-Day F/U Visit ^a
Informed consent ^c	X													
Inclusion/exclusion criteria	X	X												
EASI	X	X	X	X	X	X	X	X	X	X	X	X	X	X
BSA	X	X	X	X	X	X	X	X	X	X	X	X	X	X
IGA	X	X	X	X	X	X	X	X	X	X	X	X	X	X
SCORAD		X	X	X	X	X	X	X	X	X	X	X	X	X
Alcohol and nicotine use	X													
Patient questionnaires ^d DLQI		X					X				X	X		
Patient questionnaires ^d Daily Pruritus NRS, PGIS, ADerm-SS, and ADerm-IS	X	X	X	X	X	X	X	X	X	X	X	X		X ^d
Patient questionnaires ^d MOS Sleep Scale POEM		X					X		X		X	X ^d		X
Patient questionnaires ^{d,e} Asthma Symptoms and Daytime Nasal Symptoms	X	X					X				X			
Actigraphy Device Download		X	X	X	X	X	X							
Medical/surgical history ^f	X	X												

Table 2. Study Activities (Continued)

Activity	Screening	BL	Wk 2	Wk 4	Wk 8	Wk 12	Wk 16	Wk 20	Wk 24	Wk 32	Wk 40	Every 12 Weeks ^x or PD ^a	4 Weeks Post Topical Rescue Visit ^y	30-Day F/U Visit ^a
AE assessment ^g	D -35 to D -1	X	X	X	X	X	X	X	X	X	X	X	X	X
Only SAEs and Protocol-related nonserious AEs														
Prior/concomitant therapy	X	X	X	X	X	X	X	X	X	X	X	X	X	X
Latent TB risk factor questionnaire ^h	X													
Central lab QuantIFERON-TB Gold test (or local PPD skin test) ^h	X													
Chest x-ray ⁱ	X													
12-lead ECG ^j	X						X							
Height (screening only) and weight	X	X	X	X	X	X	X	X	X	X	X	X	X	X
Vital signs ^k	X	X	X	X	X	X	X	X	X	X	X	X	X	X
Physical exam ^l	X	X					X		X		X	X		
Serum pregnancy test at central lab ^m	X										X	X ^m		
Pregnancy test ^{n,o}		X	X	X	X	X	X	X	X	X	X	X	X	X
Lab Tests	X	X	X	X	X	X	X	X	X	X	X	X	X	X
hsCRP ^p														
Blood chemistry ^q														
Hematology (CBC)														
Urinalysis ^r														

Table 2. Study Activities (Continued)

Activity	Screening	BL	Wk 2	Wk 4	Wk 8	Wk 12	Wk 16	Wk 20	Wk 24	Wk 32	Wk 40	Every 12 Weeks ^x or PD ^a	4 Weeks Post Topical Rescue Visit ^y	30-Day F/U Visit ^a
HIV ¹ /HBV/HCV screenings	X					X ^s			X ^s					
Blood samples for ABT-494 PK assay			X ^u	X ^u	X ^v	X ^v	X ^v	X ^v	X ^v		X ^v	X ^v		
Blood samples for TBNK immunophenotyping		X			X		X	X						
Blood samples for exploratory research and validation studies (optional for some sites – see table for optional samples below) ^w		X	X	X			X	X						
Skin biopsies for exploratory research and validation studies (optional for some sites – see Table 3 for optional samples below) ^w		X		X			X							
Study Drug Dispensing/Administration		X		X	X	X	X	X	X	X	X	X ^z		
Dispense hand-held ePRO (includes subject diary) and actigraphy device	X													
Subject Diary Review			X	X	X	X	X	X	X	X	X			

Table 2. Study Activities (Continued)

- ADerm-IS = Atopic Dermatitis Impact Scale; ADerm-SS = Atopic Dermatitis Symptom Scale; BL = Baseline Visit; BSA = body surface area; CBC = complete blood count; D = Day; DLQI = Dermatology Life Quality Index; EASI = Eczema Area and Severity Index; ECG = electrocardiogram; F/U = Follow-Up; HBV = hepatitis B virus; HCV = hepatitis C virus; HIV = human immunodeficiency virus; hsCRP = high-sensitivity C reactive protein; IGA = Investigator's Global Assessment; MOS = Medical Outcomes Study; NRS = Numerical Rating Scale (for pruritus); PD = Premature Discontinuation; PGIS = Patient Global Impression of Severity; PK = pharmacokinetics; POEM = Patient Oriented Eczema Measure; PPD = purified protein derivative; PtGA = Patient's Global Assessment; SAE = serious adverse event; SCORAD = Scoring atopic dermatitis; TB = tuberculosis; Wk = Week
- a. This visit is 30 days (\pm 3 days) after last dose of study drug. For those subjects who prematurely discontinue the study, if the subject is willing, a 30-day follow-up visit (or phone call if a visit is not possible) may occur to determine the status of any ongoing AEs/SAEs or the occurrence of any new AEs/SAEs. If a subject is discontinued from study drug, the procedures outlined for the Premature Discontinuation visit (PD visit) should be completed as soon as possible, preferably within 2 weeks of study drug discontinuation.
 - b. The Baseline visit procedures will serve as the reference for all subsequent visits with the exception of the ECG which will be obtained at Screening only and used as the baseline reference.
 - c. Obtain prior to performing any study-related procedures.
 - d. Prior to other procedures; except for the questionnaires on the electronic hand-held device given to subjects to take home at Screening: daily Pruritus NRS, ADerm-SS and ADerm-IS Hand-held device usage stops at the Week 40 visit. Starting at the Week 52 visit, the questionnaires on the hand-held device (Pruritus NRS, ADerm-SS and ADerm-IS) will be given on the tablet during site visits. The MOS Sleep Scale questionnaire will stop at the Week 40 visit. The PGIS, POEM and DLQI questionnaires will be given on the tablet at site visits throughout the study.
 - e. Asthma Symptoms and Daytime Nasal Symptoms questionnaires are collected only for subjects with symptoms of asthma or rhinitis, respectively, at Screening and stop at the Week 40 visit.
 - f. Also note herpes zoster and hepatitis B vaccination status in medical history.
 - g. Collect SAEs and protocol-related nonserious AEs that occur after a subject signs the informed consent, prior to the first dose of study drug.
 - h. Refer to Section 5.3.1.1 Study Procedures TB Testing for specific requirements for TB testing and TB prophylaxis.
 - i. The screening chest x-ray will not be required if a subject had a previous normal chest-x-ray within 90 days of Screening, provided that all source documentation is available at the site.
 - j. For subjects with a normal ECG taken within 90 days of Screening, a repeat ECG at Screening will not be required, provided all source documentation is available.
 - k. Blood pressure, pulse rate, body temperature, and respiratory rate should be performed before blood draws are performed.

Table 2. Study Activities (Continued)

- l. A full physical exam is required at the visits indicated. A symptom-directed physical exam may be performed when necessary.
- m. For all females, collect serum for pregnancy test at screening and the Week 88 or PD visit. If serum pregnancy test comes back indeterminate or positive, a repeat test is necessary (pregnancy is an exclusion criterion); see Section 5.3.1.1 and Section 6.1.6 for details.
- n. Urine pregnancy test will be performed locally at every visit for all women of childbearing potential. If urine pregnancy test (which is performed at the site) is negative, begin or continue dosing. If urine pregnancy test is positive, withhold dosing and perform a serum pregnancy test. Pregnant subjects must discontinue from the study.
- o. If time between visits is longer than 1 month, then collect the results of the monthly at home urine pregnancy test between scheduled visits (see Section 5.3.1.1). If a urine pregnancy test is positive, the subject must stop dosing, come in to the clinic and have blood drawn for a serum pregnancy test that will be analyzed at the central laboratory. A pregnant or breastfeeding female will not be eligible for participation or continuation in this study. The monthly at home tests between scheduled on-site visits are to occur at Weeks 28 and 36; unless an on-site visit is necessary due to rescue therapy with topical corticosteroids per Section 5.2.3.4.
- p. hsCRP results will remain blinded to the Sponsor, Investigator, study site personnel, and subject for all visits except Screening. Investigators should refrain from locally and periodically testing hsCRP and serum amyloid A. Investigators should also refrain from locally testing procalcitonin except for safety evaluations of signs and symptoms of infection or adverse events.
- q. Minimum 8-hour fast. If a subject is not able to fast when necessary, due to unforeseen circumstances, the non-fasting status will be recorded in study source documentation.
- r. A urine dipstick macroscopic urinalysis will be completed by the central laboratory at all required visits. A microscopic analysis will be performed in the event the dipstick results show leukocytes, nitrite, protein, ketones, or blood greater than negative or glucose greater than normal.
- s. For Japan only: for subjects with HBs Ab+ and/or HBc Ab+ at Screening, the HBV-DNA PCR test should be performed again at Week 12 and Week 24. In cases where the recurrence of HBV-DNA is observed, the subject should be discontinued from the study drug. Retesting at Week 12 and Week 24 is not necessary for subjects that have a history of HBV vaccine and are HBs Ab+.
- t. HIV testing will be performed at Screening. The Investigator must discuss any local reporting requirements to local health agencies with the subject. The site will report confirmed positive results to their health agency per local regulations, if necessary. If the result is confirmed as positive, then the Investigator will discuss with the subject potential implications to the subject's health and next steps. If a subject has a confirmed positive result, the Investigator must discuss with the subject the potential implications to the subject's health and subject should receive or be referred for clinical care promptly. This testing is to be done at the central lab. A subject will not be eligible for study participation if test results indicate a positive HIV infection. AbbVie will not receive results from the testing and will not be made aware of any positive result.
- u. At Week 2 and Week 4 visits, PK samples should be collected prior to dosing and the subjects should take the study drug dose at the clinic after collecting the PK blood sample. However, if the subject normally takes the study drug dose at a time that is after the time of the scheduled study visit, the subject should follow the regular dosing schedule and the PK sample will be collected at any time during the visit.

Table 2. Study Activities (Continued)

- v. PK samples will be collected at any time during the visit. Subject should follow the regular dosing schedule.
- w. Samples only collected if subject provides written consent. Subjects should be in fasting condition (8 hours, except for water) prior to samples collection. For selected sites, these assessments (blood samples and skin biopsies collection) will be made mandatory as part of the main study.
- x. Visits are every 12 weeks from the Week 40 visit to the Week 88 visit (Wk 52, Wk 64, Wk 76, and Wk 88).
- y. A visit will be required 4 weeks after receiving topical rescue therapy. After this visit, patients will continue to follow the standard protocol visit schedule, as applicable from that date (Wk 32, Wk 40, Wk 52, Wk 64, Wk 76, and Wk 88).
- z. Study Drug Dispensing stops at the Week 76 visit.

Note 1: Visit window is ± 3 days for Period 1 (Weeks 2, 4, 8, 12 and 16) and ± 5 days for Period 2 (Weeks 20, 24, 32, 40, 52, 64, 76 and 88) and a visit 4 weeks following topical rescue if applicable. Any of the procedures may be performed at the discretion of the investigator. Subjects who choose to discontinue study drug treatment, but continue to participate in the study, should complete a Premature Discontinuation Visit (PD Visit) as soon as possible, preferably within 2 weeks. Afterwards, subjects should follow the regular visit schedule and adhere to all study procedures except for dispensing study drug, PK sample collection, and blood and skin sample collection for exploratory research and validation studies. In addition, all future rescue and efficacy-driven discontinuation criteria no longer apply.

Note 2: Twice daily use of an additive-free, bland emollient is required for at least 7 days prior to Baseline and during the study.

Table 3. Study Activities – Optional and Mandatory Samples for Exploratory Research and Validation Studies

Activity	Screening D -30 to D -1	BL	Wk 2	Wk 4	Wk 8	Wk 12	Wk 16	Wk 20	Wk 24	Wk 32	Wk 40	Every 12 Weeks or PD ^a D365 – D617	4 Weeks Post Topical Rescue Visit	30- Day F/U Visit
Pharmacogenetic samples ^a		X												
Epigenetic samples ^a		X	X	X			X	X						
Transcriptomic and epigenetic samples ^a		X	X	X			X	X						
Plasma samples for analyses including, but not limited to, proteomic and targeted protein investigations ^a		X	X	X			X	X						
Serum samples for analyses including, but not limited to, proteomic and targeted protein investigations ^a		X	X	X			X	X						
Sample for PBMC assays ^a		X		X			X							
Skin Biopsies for analyses including, but not limited to, epigenetics, transcriptomics, proteomics, immunohistochemistry ^{a,b} and targeted investigations		X		X			X							

BL = Baseline Visit; D = Day; F/U = Follow-Up; PBMC = Peripheral Blood Mononuclear Cell; PD = Premature Discontinuation; Wk = Week

- Based on the value of the different technologies, samples may also be used to assess other biomarker signatures, including but not limited to metabolomics, lipidomics, and other approaches. Samples may be used for assay of study drugs if needed.
- Subjects may still participate in the optional exploratory research/validation studies if they decide not to participate in this optional collection of biopsies. In selected sites all samples in [Table 3](#), including biopsies, will be made mandatory as part of the main study.

Table 3. Study Activities – Optional and Mandatory Samples for Exploratory Research and Validation Studies (Continued)

Note 1: Collections to be performed only if subject provides separate written consent to collect the exploratory research/validation studies samples; if the consent is not signed, no samples can be collected. It is preferred that the subject has fasted (8 hours, except for water) prior to sample collection, however it is not required. It must be recorded whether the subject has fasted or not at the time of collection.

Note 2: Selected sites will be asked to perform a complete investigation of biomarkers. For such sites, all samples in [Table 3](#) will be made mandatory as part of the main study. There will be a specific ICF for subjects in these selected sites.

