Period 2 will begin after the Week 16 Visit and will end at the Week 88 Visit. At the Week 16 Visit, subjects will be re-randomized as described in Section 5.1. During Period 2 of the study, subjects will visit the study site at Weeks 20, 24, 32, 40, 52, 64, 76, and 88. A \pm 5 day window is permitted around scheduled study visits. Subjects will start on their assigned treatment at the Week 16 visit.

The last dose of study drug is taken the day prior to the Week 88 visit.

Twice daily use of an additive-free, bland emollient is required throughout Period 2.

Discontinuation of Study Drug and Continuation of Study Participation

Subjects may discontinue study drug treatment, but may choose to continue to participate in the study (refer to Section 5.4.1 for additional details). Subjects who prematurely discontinue study drug should complete a Premature Discontinuation Visit (PD visit) as soon as possible, preferably within 2 weeks. Afterwards, subjects should follow the regular visit schedule as outlined in Table 2 and adhere to all study procedures except for dispensing study drug, PK sample collection, and blood and skin biopsy sample collection for optional exploratory research and validation studies. In addition, all future rescue and efficacy-driven discontinuation criteria no longer apply.

In Period 1, discontinuation from study drug will be mandatory for any subject with an EASI score worsening of 25% or more compared with their Baseline EASI score at any 2 consecutive scheduled study visits from Week 4 to Week 12.

In Period 2, discontinuation from study drug will be mandatory for subjects with < EASI 50 response compared with their Baseline EASI score 4 weeks following rescue with topical corticosteroids or at any visit thereafter.

Premature Discontinuation of Study (Withdrawal of Informed Consent)

Subjects may withdraw from the study completely (withdrawal of informed consent) for any reason at any time (refer to Section 5.4.2 for additional details). If a subject prematurely discontinues study participation (withdrawal of informed consent), the procedures outlined for the Premature Discontinuation visit (PD visit) should be completed as soon as possible, preferably within 2 weeks of study drug discontinuation. In addition, if the subject is willing, a 30-day follow-up visit (or phone call if a visit is not possible) may occur to determine the status of any ongoing AEs/SAEs or the occurrence of any new AEs/SAEs.

Follow-Up Period

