- If the baseline urine pregnancy test performed at the site is negative, then dosing with study drug may begin. If the baseline urine pregnancy test performed at the site is positive, dosing with study drug must be withheld and a serum pregnancy test is required. The serum pregnancy test will be sent to and performed by the central laboratory. If the serum pregnancy test is positive, study drug must be withheld and the subject must be discontinued from the study. In the event a pregnancy test comes back borderline, a repeat test is required.
- If a urine pregnancy test post baseline is positive, study drug needs to be temporarily discontinued and a serum pregnancy test is required. The serum pregnancy test will be sent to and performed by the central laboratory. If the serum pregnancy test is positive, study drug must be permanently discontinued.

In Period 2, for women of childbearing potential, a urine pregnancy test will be performed at all visits and monthly at home between scheduled study visits (at Weeks 28 and 36 at home, unless an on-site visit is necessary due to rescue therapy with topical corticosteroids per Section 5.2.3.4). The results of the monthly at home tests will be communicated to the site. If a urine pregnancy test is positive, the subject must stop dosing, come in to the clinic and have blood drawn for a serum pregnancy test that will be analyzed at the central laboratory.

At each visit, the study staff should review the pregnancy avoidance recommendations with each subject of childbearing potential and male subjects with a partner of childbearing potential, and document this discussion in the subject's source records.

A pregnant or breastfeeding female will not be eligible for participation or continuation in this study.

Clinical Laboratory Tests

Blood and urine samples will be obtained for clinical laboratory tests listed in [Table 4](#). Samples will be obtained at the designated study visits in [Table 2](#).

Unscheduled clinical labs may be obtained at any time during the study if deemed appropriate per Investigator's discretion. A certified central laboratory will be utilized to process and provide results for the clinical laboratory tests. All abnormal laboratory tests that are considered clinically significant by the investigator will be followed to a satisfactory resolution.

The central laboratory chosen for this study will provide instructions regarding the collection, processing, and shipping of these samples.

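### The named home pregnancy-test weeks end at Week 36, although the monthly rule beside them implies eight more, through Week 84

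*Protocol*

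**What the plan says.** Two places in the protocol govern home pregnancy testing in women of childbearing potential.

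- Section 5.3.1, Table 2 footnote o, gives a general rule: "If time between visits is longer than 1 month, then collect the results of the monthly at home urine pregnancy test between scheduled visits". Later in the same footnote it fixes the dates: "The monthly at home tests between scheduled on-site visits are to occur at Weeks 28 and 36". The only exception is an on-site visit made necessary by topical corticosteroid rescue.
- Section 5.3.1.1, Pregnancy Test, asks for urine tests at all Period 2 visits and "monthly at home between scheduled study visits (at Weeks 28 and 36 at home", with the same exception.

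The schedule these rules must cover is set elsewhere.

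- Table 2 footnote x: "Visits are every 12 weeks from the Week 40 visit to the Week 88 visit".
- Section 5.1, on Period 2: "The last dose of study drug is taken the day prior to the Week 88 visit".

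Neither document names a home-test week after Week 36.

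**The concern.** In both places the two weeks are written as the schedule, not as examples. They fit a visit plan that ends at Week 40, but visits and dosing continue for another 48 weeks at 12-week spacing. After Week 40 the rule and the list therefore give different schedules.

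The rationale for the exclusion criteria (Section 5.2.2) describes the drug as teratogenic in rats and rabbits, with unknown impact on human pregnancies. Between visits, a positive home test is what tells a woman to stop dosing and come in for a serum test. If a site works from the named weeks, that trigger is missing inside each 12-week gap while she takes drug at home. Two sites could follow different schedules and each claim compliance. A monitor could not say whether a missing Week 44 test is a deviation.

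**Working it through.** **Inputs**

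- Period 2 starts at Week 16, with visits at Weeks 20, 24, 32, 40, 52, 64, 76 and 88 (Section 5.1).
- The Period 2 visit window is plus or minus "5 days for Period 2 (Weeks 20, 24, 32, 40, 52, 64, 76 and 88") (Table 2, Note 1).
- The named home tests are Weeks 28 and 36 (footnote o; Section 5.3.1.1).
- Assumption: a month is 4 weeks. This is the spacing that the named weeks themselves produce.

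**Step 1: reproduce the list.** Place a home test every 4 weeks strictly inside each gap longer than 4 weeks. With the schedule cut at Week 40, the result is Weeks 28 and 36, exactly the named list.

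**Step 2: apply the same rule to Week 88.**

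| Gap (weeks) | Length (weeks) | Home tests implied | Named |
|---|---|---|---|
| 16–20, 20–24 | 4 each | none | none |
| 24–32 | 8 | 28 | 28 |
| 32–40 | 8 | 36 | 36 |
| 40–52 | 12 | 44, 48 | none |
| 52–64 | 12 | 56, 60 | none |
| 64–76 | 12 | 68, 72 | none |
| 76–88 | 12 | 80, 84 | none |

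Implied: 2 × 1 + 4 × 2 = 10. Named: 2. Missing: 10 − 2 = 8.

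**Step 3: length of a month.** With a month of 28, 30 or 31 days, one test falls strictly inside a 56-day gap and two inside an 84-day gap. The total is 2 + 8 = 10 each time, so the count of eight does not depend on the definition.

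**Step 4: interval between tests after Week 40.**

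- Under the rule: 4 × 7 = 28 days, or 28 + 5 = 33 with the home test on its nominal day and the visit at the edge of its window.
- Under the list alone: 12 × 7 = 84 days, or 84 + 5 + 5 = 94 with both visits at the edges.
- Difference: 84 − 28 = 56 days; at the extremes, 94 − 33 = 61 days.

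**Step 5: extent.** The four affected gaps run from Week 40 to Week 88: (88 − 40)/72 = 48/72 = 67% of Period 2.

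**Step 6: the rescue exception.** Topical rescue adds one visit 4 weeks later. If rescue starts at Week 52, the extra visit at Week 56 splits that gap into 4 and 8 weeks. The longer part is 8 × 7 = 56 days, or 66 with windows. The other three gaps stay at 12 weeks, so the exception does not repair the list.

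**The case against.** The strongest reply is that the duty is already in the text. Footnote o opens with a rule that needs no list to operate, and Section 5.3.1.1 repeats it for Period 2. A site that follows it tests monthly to Week 88, and nothing in the documents shows that any site would do otherwise. This stands. The 84-to-94-day interval is what follows if a site puts the list above the rule; it is not the protocol's undisputed schedule. A reader might infer that the protocol stops pregnancy testing, or even home testing, at Week 36. The documents do not support that.

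Other safeguards also apply: a urine test at every visit, a serum test at Week 88 or premature discontinuation, contraception, counselling at each visit, and more frequent tests where local rules require them. These reduce the risk, but none supplies a protocol-wide test inside the 12-week gaps.

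A reader might also infer that home testing should be limited to time on drug plus 30 days, because contraception must be of a kind "that is effective from Study Day 1 (or earlier) through at least 30 days after the last dose of study drug". The documents do not support that limit. Under Table 2 Note 1, women who stop drug but stay in the study must "adhere to all study procedures except for dispensing study drug, PK sample collection" and exploratory samples. Section 6.1.6 has positive tests assessed through the final study visit, so the limit would remove tests that the present wording keeps. Nor can the 30-day follow-up be counted on for a urine test, since it may be a phone call.

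Finally, it is tempting to call the list a leftover from a shorter design. Several protocol sections still give Period 2 treatment as 24 weeks (16 + 24 = 40), whereas SAP Section 4.2 gives 72. That is a plausible inference, but the documents do not state the origin, and the point does not need it.

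**Conclusion.** The inconsistency is real and should be fixed. The named list covers two of the ten home-test weeks that the accompanying rule implies and omits eight, all after Week 40. If the list is followed over the rule, the interval between tests triples from 28 to 84 days across four gaps, which is two-thirds of Period 2, while dosing continues.

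The 28-day interval rests on reading a month as four weeks; the count of eight holds for 28, 30 or 31 days. The number of women affected is unknown, because neither document gives the number of women of childbearing potential. The defect is confined to safety monitoring: sample size, power, endpoints and analyses do not change.

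**What to change.** In Table 2 footnote o and in Section 5.3.1.1, replace Weeks 28 and 36 with Weeks 28, 36, 44, 48, 56, 60, 68, 72, 80 and 84. Alternatively, delete the week list in both places and leave the monthly rule to govern. Either way, keep the existing exception for an on-site topical-rescue visit, and add no new limit on who is tested or for how long.

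The cost is home kits and site calls: two further home tests per 12-week gap, so 2, 4, 6 or 8 for a woman followed to Week 52, 64, 76 or 88. The monthly rule already requires these. The change needs a short amendment, with ethics review as Section 9.1 provides.
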